DATE: HH:MM/DDMMYYYY

PROGRAMMING NOTE: Continue for all chemistry parameters.

Repeat for:

Table 14.3.5.2 Summary of Values and Change from Baseline for Vital Parameters (Safety Population)

Table 14.3.5.3

Electrocardiogram - Shift in Interpretation from Baseline to Day 28 (Safety Population)

Treatment	Interpretation	Baseline n	Day 28 Visit					Total n (%)
			Normal n (%)	Abnormal, NCS n (%)	Abnormal, CS n (%)	Missing n (%)		
B244	Normal	xx	xx (xx.x)	xx (xx.x)	xx (xx.x)	xx (xx.x)	xx (xx.x)	xx (xx.x)
	Abnormal, NCS	xx	xx (xx.x)	xx (xx.x)	xx (xx.x)	xx (xx.x)	xx (xx.x)	xx (xx.x)
	Abnormal, CS	xx	xx (xx.x)	xx (xx.x)	xx (xx.x)	xx (xx.x)	xx (xx.x)	xx (xx.x)
	Missing	xx	xx (xx.x)	xx (xx.x)	xx (xx.x)	xx (xx.x)	xx (xx.x)	xx (xx.x)
	Total	xx	xx (xx.x)	xx (xx.x)	xx (xx.x)	xx (xx.x)	xx (xx.x)	xx (xx.x)
Placebo	<as above>							

Source: [Listing 16.2.9.2](#)

PROGRAM NAME: XXXXXXXXXXXXXXXXXXXXXXXXXXXXXXXXX

DATE: HH:MM/DDMMYYYY

[figure not shown]

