#### **4.3 Exploratory Objectives**

- To evaluate if B244 administration on the skin twice daily for 28 days will affect the levels of inflammatory biomarkers. To explore microbial content, microbiota composition, and B244 presence/absence at baseline and Day 28.
- To evaluate the difference between daytime and nighttime ambulatory blood pressure
- To explore and compare the blood pressure change in different ethnic groups, including African American, Caucasian, Asian and Hispanic.

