1.1.2.3. Exploratory Objectives

- To evaluate if B244 administration on the skin twice daily for 28 days will affect the levels of inflammatory biomarkers. To explore microbial content, microbiota composition, and B244 presence/absence at baseline and Day 28.
- To evaluate the difference between daytime and nighttime ambulatory blood pressure (ABP).

- To explore and compare the blood pressure change in different ethnic groups, including African-American, Caucasian, Asian, and Hispanic.

This statistical analysis plan (SAP) is designed to outline the methods to be used in the analysis of study data in order to answer the study objective(s). Populations for analysis, data handling rules, statistical methods, and formats for data presentation are provided. The statistical analyses and summary tabulations described in this SAP will provide the basis for the results sections of the clinical study report (CSR) for this trial.

This SAP will also outline any differences in the currently planned analytical objectives relative to those planned in the study protocol.

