3.6. Adjustments for Covariates

Exploratory analyses will include baseline covariates which may impact the response to treatment and will include race (Black/African-American vs Non-Black/African-American), body mass index (BMI) category, and smoking status (current vs other).

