In addition to the model results, descriptive statistics will be presented by treatment for actual value and change from baseline at each visit (Days 0, 7, 14, 28, and 42). Tabulations will be performed for both the ITT and PP populations. Statistics will also be presented for the subgroups of African-American/non-African-American, pre-hypertension/Stage 1 hypertension, male/female, and age <60/ 60 subjects in the ITT population. Additionally the mean difference between the active treatment group and the placebo for each category of the subgroup along with the 95% confidence interval and p value will also be presented. In addition, mixed model analyses of change from baseline will be performed separately for the pre-hypertensive and Stage 1 subjects using both ITT and PP populations.

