Source: [Listing 16.2.6.1](#)

PROGRAM NAME: XXXXXXXXXXXXXXXXXXXXXXXXXXXXXXXXXXXXXXX

DATE: HH:MM/DDMMYYYY

PROGRAMMING NOTE: Continue for Diastolic Blood Pressure Mixed Model Analysis.

Repeat Table 14.2.1A for:

Table 14.2.1B Summary of Values and Change from Baseline for Systolic and Diastolic Blood Pressure - Mixed Model Analysis (PP Population)

Table 14.2.1C Summary of Values and Change from Baseline for Systolic and Diastolic Blood Pressure by Race - Mixed Model Analysis (ITT Population)

Table 14.2.1D Summary of Values and Change from Baseline for Systolic and Diastolic Blood Pressure by Hypertension Stage - Mixed Model Analysis (ITT Population)

Table 14.2.1E Summary of Values and Change from Baseline for Systolic and Diastolic Blood Pressure by Gender - Mixed Model Analysis (ITT Population)

Table 14.2.1F Summary of Values and Change from Baseline for Systolic and Diastolic Blood Pressure by Age Group - Mixed Model Analysis (ITT Population)

PROGRAMMING NOTE: Replace Visit with each subgroup as applicable per table title. P-values and LSMEANS are not required for any subgroups except hypertension stage.

Table 14.2.2A

Change from Baseline at Day 28 ANCOVA Model for Systolic and Diastolic Blood Pressure (ITT Population)

Parameter: Systolic Blood Pressure

		B244			
Visit	Statistic	4 Sprays (N=xx)	8 Sprays (N=xx)	All B244 (N=xx)	Placebo (N=xx)
Day 28	LS Mean (SE)	xx.x (xx.xx)	xx.x (xx.xx)	xx.x (xx.xx)	xx.x (xx.xx)
	95% CI	xx.x	xx.x	xx.x	xx.x
	LS Mean Difference (SE) (Placebo-Active)	xx.x (xx.xx)	xx.x (xx.xx)	xx.x (xx.xx)	
	95% CI for Mean Difference	Xx, xx	Xx, xx	Xx, xx	
	P-value (vs Placebo)	0.xxxxx	0.xxxxx	0.xxxxx	
	P-value (vs 8 Spray)	0.xxxxx			

LS: Least-squares. SE = Standard Error. CI = Confidence Interval.

Model: The ANCOVA model includes the change from baseline as the dependent variable, treatment and strata as factors and baseline value as a covariate.

Source: [Listing 16.2.6.1](#)

PROGRAM NAME: XXX

DATE: HH:MM/DDMMYYYY

PROGRAMMING NOTE: Continue for Diastolic Blood Pressure.

Repeat for:

Table 14.2.2B Change from Baseline at Day 28 ANCOVA Model for Systolic and Diastolic Blood Pressure (PP Population)

Table 14.2.2C Change from Baseline at Day 28 ANCOVA Model for Systolic and Diastolic Blood Pressure by Hypertension Stage (ITT Population)

Table 14.2.3A

Summary of Values and Change from Baseline for Ambulatory Blood Pressure (ABP Population)

Parameter: Systolic Blood Pressure

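### The SAP plans no blood-pressure analysis for the four ethnic groups named in its exploratory objective and no treatment-by-race, -sex or -age interaction, and its text and table shells disagree on subgroup p-values

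*SAP*

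**What the plan says.** **Objective.** SAP 1.1.2.3 states: "To explore and compare the blood pressure change in different ethnic groups, including African-American, Caucasian, Asian, and Hispanic". Protocol 4.3 names the same four groups.

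**Race coding.** SAP 3.6 codes race as a two-level covariate: Black/African-American or not. SAP 4.3.1 presents BP statistics for the "subgroups of African-American/non-African-American, pre-hypertension/Stage 1 hypertension, male/female, and age" groups, with age cut at 60. SAP 3.8 names only Black/African-American subjects. Ethnicity (Hispanic/Latino or not) is recorded separately from race, tabulated at baseline (SAP 4.2, Table 14.1.2.1A) and listed by subject (Listing 16.2.4.1). No BP table uses it.

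**Output within subgroups.** SAP 4.3.1 promises the active-minus-placebo mean difference "for each category of the subgroup along with the 95% confidence interval and p value". The programming note after Tables 14.2.1B to 14.2.1F in SAP 7.1.1 says the opposite for race, sex and age: "P-values and LSMEANS are not required for any subgroups except hypertension stage".

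**Interactions.** The mixed model in SAP 4.3.1 includes treatment-by-strata and treatment-by-strata-by-visit terms, with spray number and hypertension status as the stratification factors. The supportive ANCOVA in SAP 4.3.1.1 also has a strata-by-treatment term. The footnotes to Tables 14.2.1A and 14.2.2A list neither, and no shell has a row for such a term. For race, SAP 4.3.5 says only that it may enter the models. No treatment-by-race, -sex or -age term is named.

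**The concern.** The objective is a comparison between groups. A difference and p-value within each category does not make that comparison, because significance in one category and not in another is weak evidence that the effects differ. In a trial with about 80% power overall, each subgroup has much less, so discordant results are likely even when the effect is the same everywhere.

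The two-level race split puts Caucasian and Asian participants into one remainder, and Hispanic participants are not identified in any BP output. SAP 1.1.2.3 says the SAP will record departures from the protocol's analytical objectives, but SAP Section 5 does not mention reducing four groups to two.

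The conflict between text and shell is a separate problem. A programmer cannot satisfy both, so whether subgroup p-values appear could be decided after the results are known.

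**Working it through.** **Inputs.** From SAP 3.1: 52 evaluable per arm, effect 5.8 mmHg, SD 10.5. From SAP 3.2: two-sided alpha 0.05. The documents give no subgroup shares, so splits are assumptions and a range is shown. The calculations compare pooled B244 with pooled placebo, one test per category.

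**The plan's own figure.** SE = 10.5 × √(2/52) = 2.06. Power = Φ(5.8/2.06 − 1.96) = 80.4% (79.7% by noncentral t). The stated 80% reproduces.

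**Same effect in two halves, each tested alone (SAP 4.3.1 text followed).**
- 26 per arm in each half: SE = 10.5 × √(2/26) = 2.91.
- Power in each half = Φ(5.8/2.91 − 1.96) = 51% (49.7% by t).
- P(exactly one significant) = 2 × 0.513 × 0.487 = 50%, with no interaction present.
- At other assumed splits: 55% at 30/70 and 61% at 20/80.
- At 50/50 with SD 9 or 11: 46% or 50%.

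**No effect anywhere: chance of at least one p<0.05.**

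| Instruction followed | Categories tested | Result |
|---|---|---|
| SAP 4.3.1 text | 8 (race, stage, sex, age; two each) | 1 − 0.95^8 = 34% |
| Table 14.2.1 note | 2 (hypertension stage) | 1 − 0.95^2 = 9.75% |

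The 34% treats the eight tests as independent. They are not, since the four factors cut the same participants four ways. The Bonferroni ceiling is 8 × 0.05 = 40%. The two categories of a single factor contain different people, so 9.75% is a fair floor.

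**What an interaction estimate would deliver.** SE of the difference between two subgroup effects = √(SE_A² + SE_B²); the true interaction is set at 5.8 mmHg.

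| Assumed split | SE (mmHg) | Power | 95% CI half-width (mmHg) |
|---|---|---|---|
| 50/50 | 4.12 | 29% | 8.1 |
| 30/70 | 4.49 | 25% | 8.8 |
| 20/80 | 5.15 | 20% | 10.1 |
| 10/90 | 6.86 | 13.5% | 13.5 |

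At 50/50, the interaction detectable with 80% power is (1.96 + 0.84) × 4.12 = 11.5 mmHg. With SD 11, power at 10/90 is 12.7%.

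**The case against.** The strongest case on the other side has five parts.

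- **The models are not free of interactions.** A reader might infer that no subgroup effect is compared at all. That is wrong for hypertension stage: SAP 4.3.1 and 4.3.1.1 both carry treatment-by-strata terms. This stands. The gap for stage is in reporting; only race, sex and age have no term.
- **The table note removes p-values.** A reader might take it as evidence of testing within each category. It says the reverse for race, sex and age; the testing comes from the text of SAP 4.3.1. If the note prevails, the one-significant, one-not error cannot arise for race, and the 34% does not apply. This stands, so both figures are given.
- **The objective is not out of reach.** A reader might conclude that the four-group question cannot be answered. Race and ethnicity are collected and the objective is exploratory, so an analysis can still be added. For two disjoint categories, a reader could derive the interaction from the published differences or summary statistics. This stands: the analysis is missing from the plan, but the data are not missing.
- **The two-level split is not explicit in every table.** The by-race shells (14.2.1C, 14.2.3B) list no categories, and the demographics shell has six races. The split is the natural reading of SAP 3.6 and 4.3.1, but the documents do not prove that no other race row will appear. Undefined categories still need defining.
- **Collapsing race is pragmatic with about 104 completers.** It is, and the low power above supports that view. It favours an estimate with an interval over a test, but it does not explain keeping the four-group objective unchanged.

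**Conclusion.** The concern holds in limited form. The four-group objective has no explicit planned BP analysis, and none is planned by Hispanic ethnicity. No treatment-by-race, -sex or -age interaction is specified. The treatment-by-strata interaction that covers hypertension stage is in the models but is not shown in the shells. SAP 4.3.1 and the Table 14.2.1 note contradict each other on subgroup p-values.

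The size depends on which instruction is followed. Under the text, there is about a 50% chance of a spurious split verdict when the effect is the same in two equal halves, and about a 34% chance of at least one false positive across eight null categories. Under the note, the false-positive figure is about 10%. These rest on the SAP's SD of 10.5, an assumed equal split for the 50%, and independence for the 34% and 10%.

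This is a minor point. It touches exploratory output only and leaves the primary analysis and sample size as they are.

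**What to change.** 1. Reconcile SAP 4.3.1 with the Table 14.2.1 note. For race, sex, age and hypertension stage, report the treatment-by-subgroup estimate at Day 28 with its 95% CI, and the within-category B244-minus-placebo differences with CIs. Drop the within-category p-values and label the output exploratory.
2. Define the race categories for the by-race shells. Add BP-change rows by arm for the named race groups and, separately, for Hispanic/non-Hispanic ethnicity. The two are recorded separately and overlap, so they should not be set out as four exclusive groups.
3. Align the footnotes of Tables 14.2.1A and 14.2.2A with the models in SAP 4.3.1 and 4.3.1.1, and add a row for the treatment-by-hypertension-stage estimate.
4. If the sponsor prefers to keep only the two-level race split, record that reduction of the objective in SAP Section 5.

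The cost is a few extra model runs and table rows on data already collected. The one real downside is imprecision: the interval will be about 8 mmHg either side at best under the SAP's SD, and wider where a subgroup is small. The report should say so, so that a wide interval is not read as evidence of a uniform effect.

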### **8.3 Study Withdrawal and Withdrawal From Investigational Product and Stopping Criteria**

A participant may withdraw from the study at any time at his/her own request, or may be withdrawn at any time at the discretion of the Investigator.

Reasons for withdrawal (participants who refuse to complete any remaining study visits) or discontinuation (participants who prematurely stop the application) at any time during the study may include, but are not limited, to the following:

- For safety reasons, either at the discretion of the Investigator or at the participant's request
- For protocol violations at the discretion of AOBiome
- Due to concomitant therapy that could interfere with the results of the study (the Investigator will report all such information on the CRFs and decide, in accordance with AOBiome, whether the participant is to be withdrawn).

The reason for participant study withdrawal will be recorded in the electronic Case Report Form (eCRF). Data from participants withdrawing from the study will be considered evaluable up to the point at which they are withdrawn using the same criteria for evalutability as for participants who complete the study.

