4.4.2. Adverse Events

Adverse events will be analyzed in terms of treatment-emergent adverse events (TEAEs) which are defined as any AEs that begin or worsen on or after the start of study drug through 30 days after the last dose of study drug.

A treatment-related TEAE is defined as a TEAE that was considered by the Investigator to be at least possibly related to the study drugs.

If a subject experiences the same AE more than once with different toxicity grades, the event with the highest grade will be tabulated in the “by grade” tables. If a subject experiences multiple AEs under the same preferred term (SOC), the subject will be counted only once for that preferred term (SOC). In addition, AEs with a missing severity will be presented in the summary table as an intensity category of “Missing.”

An overall summary table presenting the number of subjects who experienced the following will be presented by treatment arm: any AE, any related AE, any severe AE, any serious AE, any serious related AE, any AE leading to discontinuation of study drug, and any AE leading to study discontinuation.

The incidence of TEAEs will be summarized by MedDRA SOC and preferred term. Tables summarizing the incidence of TEAEs will be generated for each of the following:

- All TEAEs
- TEAEs reported as treatment-related
- Severe or Grade 3/4 TEAEs

If no subjects experience any of the events in the overall summary table, the corresponding table by SOC and preferred term will not be produced.

No formal hypothesis-testing analysis of AE incidence rates will be performed.

All AEs occurring on-study will be listed in subject data listings.

By-subject listings also will be provided for the following: subject deaths, serious AEs, and AEs leading to withdrawal.

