Subjects with at Least 1 Serious TEAE	n (%)	xx (xx.x)	xx (xx.x)	xx (xx.x)	xx (xx.x)	xx (xx.x)
Subjects with at Least 1 Treatment-Related Serious TEAE	n (%)	xx (xx.x)	xx (xx.x)	xx (xx.x)	xx (xx.x)	xx (xx.x)

If a subject experiences multiple occurrences in the category of Adverse event , the subject will be counted only once for that PT/SOC.

If a subject experiences the same AE more than once with different CTCAE grades, the event with the highest grade will be tabulated. TEAE is defined as any AEs that begin or worsen on or after the start of study drug through 30 days after the last dose of study drug. Treatment-related TEAE is defined as TEAE that was considered by the Investigator to be at least possibly related to the study drug. Severity will be graded based on the NCI CTCAE, Version 4.03.

Adverse events are coded using MedDRA v19.0.

Source: [Listing 16.2.7.1](#)

PROGRAM NAME: XXXXXXXXXXXXXXXXXXXXXXXXXXXXXXXXXXXXXXX

DATE: HH:MM/DDMMYYYY

Table 14.3.1.2

Treatment-Emergent Adverse Events (TEAE) by MedDRA System Organ Class and Preferred Term (Safety Population)

		B244				Overall (N=xx)
Statistic		4 Sprays (N=xx)	8 Sprays (N=xx)	All B244 (N=xx)	Placebo (N=xx)	
Any TEAE	n (%)	xx (xx.x)	xx (xx.x)	xx (xx.x)	xx (xx.x)	xx (xx.x)
System Organ Class 1						
Preferred Term 1	n (%)	xx (xx.x)	xx (xx.x)	xx (xx.x)	xx (xx.x)	xx (xx.x)
Preferred Term 2	n (%)	xx (xx.x)	xx (xx.x)	xx (xx.x)	xx (xx.x)	xx (xx.x)
Etc.						
System Organ Class 2						
Preferred Term 1	n (%)	xx (xx.x)	xx (xx.x)	xx (xx.x)	xx (xx.x)	xx (xx.x)
Preferred Term 2	n (%)	xx (xx.x)	xx (xx.x)	xx (xx.x)	xx (xx.x)	xx (xx.x)
Etc.						

TEAE is defined as any AEs that begin or worsen on or after the start of study drug through 30 days after the last dose of study drug. If a subject experiences multiple occurrences in the same PT/SOC, the subject will be counted only once for that PT/SOC.

Adverse events are coded using MedDRA v19.0.

Source: [Listing 16.2.7.1](#)

PROGRAM NAME: XXXXXXXXXXXXXXXXXXXXXXXXXXXXXXXXXXXXXXX

DATE: HH:MM/DDMMYYYY

Repeat Table 14.3.1.2 for the following tables:

Table 14.3.1.3 Treatment-Related Treatment-Emergent Adverse Events (TEAE) by MedDRA System Organ Class and Preferred Term (Safety Population)

PROGRAMMING NOTE: filter for at least possibly related to the study drug. Add footnote "Treatment-related TEAE is defined as TEAE that was considered by the Investigator to be at least possibly related to the study drug."

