Table 14.3.1.4 Grade 3 or 4 Treatment-Emergent Adverse Events (TEAE) by MedDRA System Organ Class and Preferred Term (Safety Population)

PROGRAMMING NOTE: filter for grade = 3 or 4. Add footnote "Severity will be graded based on the NCI CTCAE, Version 4.03." AND "If a subject experiences the same AE more than once with different CTCAE grades, the event with the highest grade will be tabulated."

Table 14.3.1.5 Treatment-Related Grade 3 or 4 Treatment-Emergent Adverse Events (TEAE) by MedDRA System Organ Class and Preferred Term (Safety Population)

PROGRAMMING NOTE: filter for grade = 3 or 4 and at least possibly related to the study drug. Add footnote "Treatment-related TEAE is defined as TEAE that was considered by the Investigator to be at least possibly related to the study drug." AND "Severity will be graded based on the NCI CTCAE, Version 4.03." AND "If a subject experiences the same AE more than once with different CTCAE grades, the event with the highest grade will be tabulated."

Table 14.3.1.6 Serious Treatment-Emergent Adverse Events (TEAE) by MedDRA System Organ Class and Preferred Term (Safety Population)

PROGRAMMING NOTE: filter for SERIOUS = YES.

Repeat Listing 16.2.7.1 for the below table listings.

Table 14.3.2.1 Serious Adverse Events

PROGRAMMING NOTE: filter for SERIOUS = YES and remove Serious? Column.

Table 14.3.2.2 Adverse Events Leading to Early Discontinuation

PROGRAMMING NOTE: filter for subjects who discontinued early.

Table 14.3.2.3 Subject Deaths

PROGRAMMING NOTE: filter for subject deaths, remove Outcome column and accompanying footnote and renumber other footnotes accordingly.

Table 14.3.5.1

Summary of Values and Change from Baseline for Chemistry Parameters (Safety Population)

Parameter: xx

B244									
Visit	Statistic	4 Sprays (N=xx)		8 Sprays (N=xx)		All B244 (N=xx)		Placebo (N=xx)	
		Value	Change from Baseline	Value	Change from Baseline	Value	Change from Baseline	Value	Change from Baseline
Baseline	n	xx	-	xx	-	xx	-	xx	-
	Mean	xx.x		xx.x		xx.x		xx.x	
	(SD)	(xx.xx)		(xx.xx)		(xx.xx)		(xx.xx)	
	Median	xx.x		xx.x		xx.x		xx.x	
	Min, Max	xx, xx		xx, xx		xx, xx		xx, xx	
Day 28	n	xx	xx	xx	xx	xx	xx	xx	xx
	Mean	xx.x	xx.x	xx.x	xx.x	xx.x	xx.x	xx.x	xx.x
	(SD)	(xx.xx)	(xx.xx)	(xx.xx)	(xx.xx)	(xx.xx)	(xx.xx)	(xx.xx)	(xx.xx)
	Median	xx.x	xx.x	xx.x	xx.x	xx.x	xx.x	xx.x	xx.x
	Min, Max	xx, xx	xx, xx	xx, xx	xx, xx	xx, xx	xx, xx	xx, xx	xx, xx

Source: [Listing 16.2.8.1.1](#), [Listing 16.2.8.1.2](#)

PROGRAM NAME: XXX

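### The SAP's listing of adverse events leading to discontinuation selects subjects rather than events, and the by-arm counts and SOC/PT summary of those events have no planned table

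*SAP*

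**What the plan says.** **The listing.** In SAP section 7.1.1, Tables 14.3.2.1 to 14.3.2.3 are introduced with "Repeat Listing 16.2.7.1 for the below table listings". They are therefore by-subject AE listings, not counts. For Table 14.3.2.2, on AEs leading to early discontinuation, the programming note is "filter for subjects who discontinued early".

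**What the SAP text asks for.** Section 4.4.2 states: "By-subject listings also will be provided for the following: subject deaths, serious AEs, and AEs leading to withdrawal". Section 3.2 likewise plans a listing of AEs leading to discontinuation. Section 4.4.2 also plans an overall summary by arm whose last two categories are "any AE leading to discontinuation of study drug, and any AE leading to study discontinuation".

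**What the protocol asks for.** Section 15.3 includes discontinuations due to AEs among its separate tabulations. Section 15.3.5 asks for an incidence summary of AEs leading to discontinuation. Section 15.3.7 asks that AEs leading to treatment discontinuation be summarised overall and by SOC and PT.

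**Why subjects may stop.** Protocol section 8.3 lists safety reasons, but also "For protocol violations at the discretion of AOBiome" and concomitant therapy that could interfere with the results. It separates withdrawal from the study from "discontinuation (participants who prematurely stop the application").

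**The concern.** A listing whose title states a cause should be selected on that cause. Selecting on subject status puts unrelated AEs, such as a cold in someone withdrawn for a protocol violation, under a title saying that they led to discontinuation.

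This would matter less if a summary table gave the correct counts, but none does. Safety and tolerability is the first primary objective, its endpoint is adverse events, and stopping because of an AE is one of the most direct measures of tolerability. With the shells programmed as drawn, the report would contain no by-arm count of subjects who stopped for an AE, and the one output carrying that title would mix caused and unrelated events.

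**Working it through.** The plan gives no figure to reproduce here. The check sets each requirement beside the output meant to meet it.

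**1. The filter.** The note for Table 14.3.2.1 selects on an AE field (serious = yes). The note for Table 14.3.2.2 selects on the subject. The source, Listing 16.2.7.1, has an Action Taken column with a code for drug stopped and a Discontinued from Study column, so an AE-level filter was available. Taken literally, the note can err in two directions:
- Over-inclusion: all AEs of subjects who stopped for non-AE reasons allowed by Protocol 8.3.
- Omission: if stopping early means leaving the study, AEs that stopped the product in subjects who stayed.

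**2. The by-arm counts.** SAP 4.4.2 names seven categories. Shell 14.3.1.1 has six rows, ending with "Subjects with at Least 1 Treatment-Related Serious TEAE".

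| SAP 4.4.2 category | Row in shell 14.3.1.1 |
|---|---|
| Any AE | Yes |
| Related | Yes |
| Severe | In part (Grade 3 or 4) |
| Serious | Yes |
| Serious and related | Yes |
| Led to stopping the drug | None |
| Led to leaving the study | None |

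Matched 4, partly matched 1, absent 2: 4 + 1 + 2 = 7. The shell's sixth row, related Grade 3 or 4, has no counterpart in the text.

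**3. Can another table supply them?** The disposition shell (Table 14.1.1) gives as reasons death, loss to follow-up, consent withdrawal, investigator's decision, screen failure and other. It has no adverse-event reason, so the missing counts cannot be read from it.

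**4. The protocol's tabulations.** Protocol 15.3 names five: treatment-emergent AEs, related AEs, SAEs, discontinuations due to AEs, and Grade 3 or above. SAP 3.2 keeps three, dropping SAEs and discontinuations. The output list has five SOC/PT tables (14.3.1.2 to 14.3.1.6): all, related, Grade 3 or 4, related Grade 3 or 4, and serious. SAEs are thus restored and discontinuations are not. SAP section 5 records no change on this point, although SAP 1.1.2.3 says that the SAP will set out differences from the protocol.

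**5. Size.** Protocol section 6 plans to enrol 116 and complete 104. Planned study exits: 116 − 104 = 12, and 12/116 = 10.3%. This is a ceiling for wrongly listed study exits, since a dropout with no AE has no row and some exits may be AE-driven. The documents do not give the AE-driven share, or the number who stop the product but stay on study.

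**6. A related inconsistency.** Protocol 15.3 and SAP 3.2 say Grade 3 or higher. SAP 4.4.2 says severe or Grade 3/4. Tables 14.3.1.1, 14.3.1.4 and 14.3.1.5 use Grade 3 or 4, which leaves out an event graded 5.

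**The case against.** The strongest defence is that the note is terse rather than wrong. The table's title, SAP 3.2 and SAP 4.4.2 all say that the output concerns AEs leading to discontinuation, and Listing 16.2.7.1 has a Discontinued from Study column. A careful programmer could take the note as an instruction to filter on that column. This is possible, but the note does not say so, and the SAP does not state whether that column is recorded per AE or per subject. If it is per subject, filtering on it selects the same records as the literal reading.

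It can also be said that all on-study AEs are listed under treatment headings, so with few discontinuations the counts could be recovered by hand, and that programmers may follow the SAP text over the shell. Both are fair, and they limit the consequence. They do not remove the conflict between text and shell.

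Three stronger readings are tempting and not supported:
- A reader might infer that SAP 4.4.2 itself requires the SOC/PT table. It names only three such tables (all, related, severe or Grade 3/4) and, for withdrawals, a listing. Its sentence that, where there are no events, "the corresponding table by SOC and preferred term will not be produced" hints at more but does not list one. The explicit requirement is in Protocol 15.3.7.
- A reader might infer that about 12 subjects would be listed wrongly. Twelve is a ceiling from the dropout allowance, not an estimate.
- A reader might infer that a fatal event could vanish from the report. It would still appear in the serious-event SOC/PT table (14.3.1.6), the SAE listing (14.3.2.1) and the death listing (14.3.2.3).

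**Conclusion.** The point holds as a safety-reporting defect. Followed as written, the note for Table 14.3.2.2 gives a listing that does not match its title or SAP 3.2 and 4.4.2. Two of the seven categories in SAP 4.4.2 have no row in Table 14.3.1.1 and cannot be taken from the disposition table. One of the five tabulations in Protocol 15.3, with the SOC/PT summary of Protocol 15.3.7, has no listed table and no declared removal.

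This rests on reading the note literally and on the shells being programmed as drawn. The AE data are not lost, and efficacy and power are untouched. The number of affected subjects cannot be derived, beyond the ceiling of about 12 study exits at the planned dropout. The severity-grade mismatch is a secondary consistency matter. It is worth correcting before the tables are programmed.

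**What to change.** - **Table 14.3.2.2:** filter at AE level, on Action Taken = Stop or Discontinued from Study = yes. First confirm that the second field is recorded per AE; if it is a subject-level flag, it cannot show which AE led to exit and would bring the problem back.
- **Table 14.3.1.1:** add the two SAP 4.4.2 rows, for an AE leading to discontinuation of study drug and an AE leading to study discontinuation.
- **SOC/PT summary:** add the Protocol 15.3.7 table to SAP 3.2, SAP 4.4.2 and the output list, subject to the existing rule that no table is produced when there are no events. Otherwise declare its removal in SAP section 5.
- **Secondary:** use one rule, Severe or Grade 3 or higher, in SAP 3.2, SAP 4.4.2 and Tables 14.3.1.1, 14.3.1.4 and 14.3.1.5.

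The cost is SAP text and programming-note edits, two rows, one table and one check of how a field is recorded. The fields are already planned in Listing 16.2.7.1. No new visit, sample or protocol amendment is needed.
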